8.2.2. Sample Size Sensitivity

If the annual rate of moderate and severe exacerbations in the FF/UMEC/VI treatment arm is different from the 0.8 used in the sample size calculation, the power to detect the change in exacerbations rates will be affected.

Table 5 illustrates the power which would be obtained from various moderate and severe exacerbation rates and rate reductions for the FF/UMEC/VI treatment arm compared with the FF/VI treatment arm. The sample size, dispersion factor and two-sided significance threshold of 1% remain fixed.

Table 5 Power for varying FF/UMEC/VI exacerbation rates and treatment improvements versus FF/VI

FF/UMEC/VI rate	True Rate of Exacerbation Improvement, FF/UMEC/VI versus FF/VI		
	8% Reduction	10% reduction	12% reduction
0.90	51%	76%	92%
0.80	47%	72%	90%
0.70	43%	67%	87%
0.60	38%	62%	82%

Table 6 illustrates the power which would be obtained from various moderate and severe exacerbation rates and rate reductions for the FF/UMEC/VI treatment arm compared with the UMEC/VI treatment arm. The sample size, randomization ratio (2:1), dispersion factor and two-sided significance threshold of 1% remain fixed.

Table 6 Power for varying FF/UMEC/VI exacerbation rates and treatment improvements versus UMEC/VI

FF/UMEC/VI rate	True Rate of Exacerbation Improvement, FF/UMEC/VI versus UMEC/VI		
	10% reduction	12% reduction	15% reduction
0.90	53%	75%	94%
0.80	49%	71%	92%
0.70	45%	66%	89%
0.60	40%	60%	85%

8.2.3. Sample Size Re-estimation

Blinded evaluation of exacerbation rates is planned for this study. A blinded evaluation of exacerbation rates for the purpose of sample size re-estimation will be done after one year of enrolment, or when 5,000 subjects have been randomized, whichever is earlier. A subsequent evaluation will be done after approximately 18 months of enrolment, or when 7,500 subjects have been randomized, whichever is earlier.

If the exacerbation rates for the study are lower than planned, a sample size re-estimation may be conducted. Any subsequent change to the planned number of subjects randomized would be documented in a protocol amendment.

8.3. Data Analysis Considerations

8.3.1. Analysis Populations

- All Subjects Enrolled Population: This population includes all subjects for whom a record exists on the study database, including screened subjects and subjects who were not screened but signed an ICF. This population will be used for the summary of subject disposition and the listing of SAEs for non-randomised subjects.
- Intent-to-Treat (ITT) Population: The ITT Population will comprise all subjects randomised to treatment apart from those randomised in error. A subject who is recorded as a screen or run-in failure and also randomised, but did not receive a dose of study treatment, will be considered to be randomised in error. Any other subject who receives a randomisation number will be considered to have been randomised. The ITT Population is the primary analysis population of interest.
- Pharmacokinetic (PK) Population: The PK Population will comprise the subset of subjects in the ITT Population for whom a PK sample was obtained and analyzed. This population will be used for all concentration-time and PK parameter tables, listings and figures.

8.3.2. Analysis Data Sets

Details of the analysis datasets to be created will be given in the RAP.

8.3.3. Treatment Comparisons

8.3.3.1. Primary Comparisons of Interest

The primary comparisons of interest will be the pair-wise comparisons of FF/UMEC/VI against FF/VI and FF/UMEC/VI against UMEC/VI. The primary comparisons will be tested for the primary endpoint, the annual rate of on-treatment moderate and severe exacerbations.

The primary analysis will be based on a two-sided hypothesis testing approach. The hypotheses associated with the statistical test of the primary efficacy endpoint are $H_0: \lambda_T/\lambda_D=1$ versus $H_A: \lambda_T/\lambda_D \neq 1$ where λ_T is the annual rate for triple therapy (FF/UMEC/VI) and λ_D is the annual rate for the respective dual therapies (FF/VI and UMEC/VI).

Both primary comparisons will be tested using the ITT population. In order to account for multiplicity, the truncated Hochberg procedure [Dmitrienko, 2008] with a truncation parameter of $\gamma=0.6$ will be used to control overall Type I error at $\alpha=0.05$.

For the primary comparisons, both comparisons will be declared statistically significant if the p-value for both comparisons is significant at the 0.04 level. Should the largest p-value for the two comparisons be above 0.04, the other comparison will be declared

statistically significant if the smaller p-value is below 0.025. If at least one of the comparisons is significant, this will allow inference of secondary endpoints.

[figure not shown]
8.3.3.2. Other Comparisons of Interest

If one or both of the primary endpoints is considered statistically significant, inferences will be made from unadjusted p-values for treatment comparisons on secondary and other endpoints. If both co-primary treatment comparisons are statistically significant, these secondary and other treatment comparisons will be declared significant if the unadjusted p-value is <0.05 . If only one co-primary treatment comparison is statistically significant, these secondary and other treatment comparisons will be declared significant if the unadjusted p-value is <0.01 .

Where strong control of type I error is required for secondary endpoints, multiplicity will be controlled using a hierarchical, closed testing procedure. The secondary hypothesis tests will be grouped sequentially in two blocks of two comparisons each, grouped according to specific clinical concepts (lung function and symptoms, and time-to-first exacerbation event). Each block of comparisons will also be adjusted for multiplicity using the truncated Hochberg method as described for the primary endpoint analysis, with a truncation parameter of $\gamma=0.6$ for the first block and a truncation parameter of $\gamma=1$ for the second block.

Within each block, at least one endpoint must be considered statistically significant in order to make inferences in the subsequent block. For example, as shown in [Figure 2](#) at least one of endpoints S1a and S1b would need to be significant in order to make inferences for the S2a/S2b comparisons contained in the next block.

Figure 2 Secondary endpoint hierarchy

Methods for handling missing data for summaries of the secondary efficacy endpoints will be detailed in the RAP.

8.3.4. Interim Analysis

An Independent Data and Monitoring Committee (IDMC) will monitor progress of the study and ensure that it meets the highest standards of ethics and patient safety. Only the IDMC will be authorized to review unblinded interim safety analyses during the trial.

This committee will be formed specifically to oversee trial progression with regards to occurrence of adverse events. The committee, which will comprise a minimum of 3 people, will include an independent statistician and an independent respiratory clinician with experience in COPD and a cardiologist.

The unblinded periodic safety updates will be performed and delivered to the IDMC by an independent Statistical Data Analysis Centre (SDAC).

The IDMC will give a recommendation to the central study team as to whether the trial should be stopped prematurely following review of the interim results for safety. The central study team will decide whether to act on this recommendation.

In the event of early stopping, subjects will be brought to the investigational sites for a final visit, where possible. The final analysis will include all data collected up to and including the final visit.

Membership, functions and operating procedures of IDMC and other organisational groups for this study will be defined in a separate document. Operating procedures for the IDMC will be established before the first review of unblinded data.

8.3.5. Key Elements of Analysis Plan

8.3.5.1. Efficacy Analyses

The primary efficacy endpoint of the annual rate of on-treatment moderate and severe exacerbations will be analyzed using a generalized linear model assuming the negative binomial distribution, with the logarithm of time on treatment as an offset variable. The model will include terms for treatment group, gender, exacerbation history (one, two or more), smoking status at screening, baseline disease severity (as % predicted FEV₁) and geographical region. The adjusted mean annual rates, pair-wise treatment ratios and associated p-values and confidence limits will be presented. The fit of the negative binomial model will be examined using “Q-Q” plots of standardized residuals with simulated envelopes.

For the co-primary endpoints, sensitivity analyses will be performed where all available data collected until the time of study withdrawal will be used. For these sensitivity analyses, the total number of events and the total time in the study (both on-treatment and post-treatment) prior to study withdrawal will be used in the analysis model. Imputations made for the period following study withdrawal will be described in the RAP. Additional sensitivity analyses using multiple imputation methods will be described in the RAP.

The secondary endpoints of trough (pre-dose AM) FEV₁ and SGRQ total score will be analysed using mixed models repeated measures with covariates of treatment group, smoking status at screening, baseline, region, and visit, plus interaction terms for visit by baseline and visit by treatment group.

The secondary endpoints involving time to first moderate and/or severe exacerbation will compare the treatment groups using Cox's proportional hazards model, adjusting for treatment group, gender, exacerbation history (one, two or more), smoking status at screening, baseline disease severity (as % predicted FEV₁), and geographical region.

Secondary and other endpoints involving the annual rate of exacerbations will be analysed as described for the primary endpoint.

The additional endpoint of time to onset of multiple moderate and severe exacerbations will be analysed using an Anderson-Gill model for time to recurrent events.

Full details of the analyses to be performed on all primary, secondary and other efficacy endpoints will be given in the RAP.

8.3.5.2. Safety Analyses

The extent of exposure to study drug will be summarized by treatment group, using the statistics n, mean, SD, median, minimum and maximum.

AEs and SAEs occurring pre-treatment, during active treatment and post-treatment will be summarized separately. The number and percentage of subjects experiencing at least one AE of any type, AEs within each body system and AEs within each preferred term will be presented for each treatment group. Separate summaries will be provided for all AEs, drug-related AEs, SAEs, and for AEs leading to permanent discontinuation of study drug or withdrawal from the study.

Time to first event in the Pneumonia Adverse Event of Special Interest subgroup and time to first serious event in the Pneumonia Adverse Event of Special Interest subgroup will be analysed using Cox's proportional hazards model. Deaths due to pneumonia will be summarised and tabulated.

Incidence of bone fractures will be summarised. Full details will be given in the RAP.

Incidence of cardiovascular events (including supraventricular arrhythmia and non-fatal myocardial infarction) will be summarised.

All laboratory parameters will be summarised and tabulated.

A pre-specified MACE analysis (broad analysis and narrow analysis) will be performed using adjudicated cardiovascular deaths and other non-fatal SAEs. MACE events to be included in both the broad and narrow analysis would be defined *a priori*.

Full details of the analyses to be performed on all safety endpoints will be given in the RAP.

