4.6. Follow-up Contact

A safety follow-up contact will be conducted 7 days (-1/+4) following the completion of the randomized treatment period (Visit 7) or following the IP Discontinuation Visit.

The follow-up contact can be made by phone call or by site visit. The following procedures will be performed:

- Adverse event assessment
- Concurrent medication assessment
- COPD exacerbation assessment
- Call IVRS to report safety follow-up contact

Subjects who have successfully completed all on-treatment randomized visits (including Visit 7) will be discharged from the study upon completion of the safety follow-up contact.

Subjects who have discontinued IP will complete the IP Discontinuation Visit followed 7 days (-1/+4) later by the safety follow-up contact but then will continue in the study to

complete all remaining visits by telephone contact and will be discharged from the study once they complete the Visit 7 telephone contact.

Subjects who are on IP and wish to withdraw from further participation in the study will complete the IP Discontinuation Visit followed 7 days (-1/+4) later by the safety follow-up contact.

Subjects who have discontinued IP and are continuing in the study by completing study-related telephone contacts (after completing their IP Discontinuation Visit and safety follow-up phone call), but who now wish to withdraw from the study, should contact the site by phone to notify the site of their intention to withdraw; no additional safety follow-up visit is required.

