- Physical examination may include height, weight, blood pressure, temperature, heart rate.
- Vital signs must be performed prior to spirometry and prior to taking morning dose of IP.

- j. ECG to be obtained 15 minutes to 45 minutes post-dose at treatment Visits 3, 5 and 7 and IP Discontinuation Visit (if applicable). In addition, at V3 (in a subset of subjects at selected sites) one additional ECG will be collected pre-dose.
- k. Chest X-ray is required at Screening (or historical x-ray obtained within 3 months prior to Screening) and at anytime there is a suspected pneumonia or a moderate/severe exacerbation.
- l. Pulse oximetry must be performed at V2 and anytime there is a suspected pneumonia or a moderate or severe exacerbation.
- m. In a subset of 300 subjects at selected sites, PK samples to be obtained at two timepoints at Visit 4: pre-dose and in the window 5 to 15 minutes post-dose.
- n. In a subset of 300 subjects at selected sites, PK samples to be obtained at two timepoints at Visit 5: 5 to 15 minutes post-dose and 45 to 90 minutes post-dose.
- o. Genetic consent must be obtained prior to obtaining a blood sample. No study centers in China will participate in genetic research in this study.
- p. Hematology and chemistry panels will include liver chemistry, and potassium and glucose levels.
- q. All female subjects of child bearing potential will have a urine pregnancy test at each visit except Visits 2 and follow-up.
- r. Subjects must withhold their morning dose of IP at each clinic visit and not take their IP dose until instructed to do so by study staff.

NOTE:

1. Subjects who have permanently discontinued IP (and have not withdrawn consent) will complete the discontinuation IP visit and the safety follow-up contact and then will continue in the study to complete all remaining per protocol scheduled visits by phone contact to collect Exacerbations, SAEs and Concomitant Medications.
2. * In China only, Serious AEs will be recorded from the time the consent form is signed until the 7-day safety follow-up visit/telephone contact has been completed, or until Visit 7(telephone contact) for subjects who have discontinued IP but continue in the study.

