6.3.9. Time Period and Frequency of Detecting AEs and SAEs

The investigator or site staff is responsible for detecting, documenting and reporting events that meet the definition of an AE or SAE.

AEs and SAEs will be collected from the time of Visit 2 (Randomization) until the 7-day safety follow-up visit/telephone contact has been completed or until Visit 7 for subjects who have discontinued IP but continue in the study. Additionally, SAEs assessed as **related** to study participation (e.g., study treatment, protocol-mandated procedures, invasive tests, or change in existing therapy) or related to a GSK concomitant medication, will be recorded from the time a subject consents to participate in the study up to and including any follow up contact. All SAEs will be reported to GSK within 24 hours, as indicated in Section 6.3.11.

All SAEs will be followed up until resolution, until the condition stabilizes, until the event is otherwise explained, or until the subject is lost to follow-up. Once resolved, the SAE eCRF page will be updated. The investigator will ensure that follow-up includes any supplemental investigations as may be indicated to elucidate the nature and/or causality of the SAE. This may include additional laboratory tests or investigations, histopathological examinations, or consultation with other health care professionals.

COPD exacerbations will be collected from the time of Visit 2 (Randomization) until the 7-day safety follow-up visit/telephone contact has been completed or until Visit 7 for subjects who have discontinued IP but continue in the study. COPD Exacerbations will not be collected as AEs unless they meet the definition of an SAE.

NOTE: In China only, Serious AEs will be recorded from the time the consent form is signed until the 7-day safety follow-up visit/telephone contact has been completed, or until Visit 7(telephone contact) for subjects who have discontinued IP but continue in the study.

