### 9.2.3. Overview of Planned Adverse Event Analyses

**Table 7 Overview of Planned Adverse Event Analyses**

	Data Displays Generated		
	Table	Figure	Listing
Adverse Events (AEs)			
Overview of On-treatment AEs	Y		
All AEs (ASE)			Y
On-treatment AEs	Y 		
On-treatment Drug-Related AEs	Y		
On-treatment AEs Leading to Permanent Discontinuation of Study Treatment or Withdrawal from the Study	Y		Y 
Ten Most Frequent On-treatment AEs in Each Treatment Group	Y		
On-treatment Common Non-Serious AEs (3% or More of Subjects in Any Treatment Group)	Y		
On-treatment AE Categories of Interest in the Elderly by Age	Y		
Relationship of AE System Organ Class, Preferred Term and Verbatim Text (ASE)	Y		
Subject Numbers for Individual AEs (ASE)			Y
Serious Adverse Events (SAEs)			
Pre-treatment SAEs	Y 		Y 
Pre-treatment Fatal SAEs (ASE)	Y		
Pre-treatment SAEs Leading to Withdrawal from Study (ASE)	Y		

	Data Displays Generated		
	Table	Figure	Listing
Subjects and Number of Occurrences of on-treatment serious, drug-related serious, fatal and drug-related SAEs	Y		
On-treatment SAE	Y 		Y 
On-treatment Drug-Related SAEs	Y		
On-treatment Drug-Related Fatal SAEs	Y		
Post-treatment SAEs	Y		Y 
Post-treatment Fatal SAEs	Y		
Reasons for Considering as a Serious AE			Y
Adjudicated Serious Adverse Reports			
Adjudicated On-treatment Serious Adverse Reports	Y 		
Adjudicated Post-treatment Serious Adverse Reports	Y 		
AEs of Special Interest (AESI)			
On-treatment AESI	Y 		
Analysis of Time to First On-treatment Event in the Pneumonia AESI Group	Y 	Y 	
Pneumonia Risk Factors at Screening for those Subjects with an on-treatment event in the pneumonia AESI group	Y 		
Analysis of Time to First On-treatment Event in the CV AESI Group	Y 	Y 	
Summary of Incidence of On-treatment Pneumonia AESI and Adjudicated Pneumonia	Y		
SAEs of Special Interest (SAESI)			
On-treatment Serious AESI	Y 		
Analysis of Time to First On-treatment event in the Pneumonia AESI group resulting in hospitalization, prolonged hospitalization or death	Y 	Y 	
Analysis of Time to First On-treatment event in the CV AESI group resulting in hospitalization, prolonged hospitalization or death	Y 	Y 	

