**11.3.2. All Cause Mortality**

For the summaries and analyses of the efficacy endpoint of all cause mortality, treatment phases will be defined as described in the table below after any imputation of partial death dates as described in Section 11.6.1:

Pre-treatment	Death Date < Treatment Start Date (i.e. subject did not start study treatment)
On-treatment	Treatment Start Date ≤ Death Date ≤ Treatment Stop Date + 7
Off-treatment	Subjects that prematurely discontinued study treatment that attended the Week 52 visit: Treatment Stop Date + 7 < Death Date ≤ date of Week 52 + 7  Subjects that prematurely discontinued study treatment that withdrew from the study prior to Week 52: Treatment Stop Date + 7 < Death Date ≤ projected Week 52 date + 7
Post-study	Subjects that completed study treatment: Death Date > Treatment Stop Date + 7  Subjects that prematurely discontinued study treatment that attended the Week 52 visit: Death Date > date of Week 52 + 7  Subjects that prematurely discontinued study treatment that withdrew from the study prior to Week 52: Death Date > projected Week 52 date + 7
Note: Study treatment completion is defined in Section 11.5.1.3. The projected Week 52 date is defined in Section 11.5.1.4.	

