**11.3.3. Other Data**

**11.3.3.1. Post-treatment and Post-study Phases**

For all events and assessments the post-treatment and post-study phases will be defined as follows:

Post/Off-treatment	Event Onset Date or Assessment Date ≥ Treatment Stop Date + 2 AND Event Onset Date or Assessment Date ≤ study conclusion date  Note: the study conclusion date reflects the safety F/U contact for study treatment completers or the maximum of (the subjects last phone contact or their last clinic visit or the date the subject was lost to follow-up) for those subjects who discontinued study treatment prematurely.
Post-study	Event Onset Date or Assessment Date > study conclusion date.  Note: this post-study data will not be included in any summaries or analyses (but will be listed)

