**11.3.3.3. Pre-treatment and On-treatment where Time is Not Recorded**

The pre-treatment and on-treatment phases will be defined as described in the table below for the following events and assessments:

- Event-based data with an onset date reported
- Unscheduled assessments that have a date reported
- Assessments for which no planned relative time is recorded in the database, the scheduled Day 1 assessment is to be performed post-dose and have a date reported

Pre-treatment	Event Onset Date or Assessment Date $<$ Treatment Start Date
On-treatment	Treatment Start Date $\leq$ Event Onset Date or Assessment Date $\leq$ Treatment Stop Date + 1 or any assessment with a missing or partial date unless there is evidence it was not on-treatment

The pre-treatment and on-treatment phases will be defined as described in the table below for the following events and assessments:

- Assessments for which no planned relative time is recorded in the database, the scheduled Day 1 assessment is to be performed pre-dose and have a date reported

Pre-treatment	Event Onset Date or Assessment Date $\leq$ Treatment Start Date
On-treatment	Treatment Start Date $<$ Event Onset Date or Assessment Date $\leq$ Treatment Stop Date + 1 or any assessment with a missing or partial date unless there is evidence it was not on-treatment

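### The protocol states a post-treatment summary of AEs as well as SAEs; the SAP tabulates post-treatment events only when serious and does not declare the change

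*Protocol*

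**What the plan says.** **Protocol, analysis.** Section 8.3.5.2 commits to three phases for both kinds of event: "AEs and SAEs occurring pre-treatment, during active treatment and post-treatment will be summarized separately". It leaves full details to the RAP.

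**Protocol, collection.** Section 6.3.9: "AEs and SAEs will be collected from the time of Visit 2 (Randomization) until the 7-day safety follow-up visit/telephone contact has been completed". For subjects who stop IP but stay in the study, the same sentence extends collection of both AEs and SAEs to Visit 7. Section 4.6 includes an adverse event assessment at the safety contact, which falls 7 days (-1/+4) after Visit 7 or the IP Discontinuation Visit. Section 4.4.2 and Note 1 to Table 4 describe the later telephone visits more narrowly. In Note 1 the remaining visits are completed "by phone contact to collect Exacerbations, SAEs and Concomitant Medications".

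**SAP, phases.** Under 11.3.3.3 an event is on-treatment if its onset is no later than "Treatment Stop Date + 1 or any assessment with a missing or partial date unless there is evidence it was not on-treatment". Under 11.3.3.1 the post-treatment phase begins at "Event Onset Date or Assessment Date ≥ Treatment Stop Date + 2" and runs to study conclusion. Section 11.5.1.5.2 defines an at-risk period for each phase. Deaths in the all-cause mortality endpoint have their own on-treatment rule in 11.3.2: "Treatment Start Date ≤ Death Date ≤ Treatment Stop Date + 7".

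**SAP, displays.** Table 7 has no post-treatment row for AEs in general. It has "Post-treatment SAEs", post-treatment fatal SAEs and adjudicated post-treatment serious reports, which become Tables 3.026, 3.027 and 3.031 to 3.033. The other AE, special-interest, MACE, pneumonia-form and fracture incidence tables are on-treatment, apart from the pre-treatment SAE tables.

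**The concern.** The protocol names a summary and collects the data for it; the SAP then leaves it out without saying so. SAP 2.1 is where departures from the protocol are recorded, and it takes the trouble to clarify the pneumonia analyses, but this omission is not there. SAP 5.2 describes post-treatment safety data as SAEs, which does not match protocol 6.3.9.

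Pneumonia and fractures are named in protocol 1.3.3 as key risks of ICS-containing combinations, and cardiovascular effects as the key risk of the LAMA/LABA component. Events of these kinds need not be serious. A non-serious one that begins shortly after the last dose would be collected and listed but not counted by arm. A serious one would be counted among SAEs but not in the displays a reader would consult for pneumonia, cardiovascular events or fractures.

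The collection rules raise a second issue. If sites read 6.3.9 literally, they record non-serious AEs to Visit 7 after early discontinuation. If they follow 4.4.2 and Note 1, they do not. The post-treatment AE data could then differ by site.

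**Working it through.** There is no plan figure to reproduce. The check is a comparison of passages followed by a size estimate.

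**1. Where a post-treatment event goes**

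| Event with onset at stop + 2 or later | Incidence table by arm | Pneumonia, CV or fracture display | Listing |
|---|---|---|---|
| Serious | Yes (3.026; 3.027 if fatal; adjudicated reports in 3.031 to 3.033) | No | Yes |
| Non-serious | None | No | Yes (18 and 19) |

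The on-treatment displays are 3.034 and 3.035 (special interest), 3.046 and 3.047 (MACE), 3.048 to 3.051 (pneumonia form) and 3.055 (fractures). Time-to-first-event analyses censor at stop + 1 (SAP 11.5.4.8). Table 3.015 shows the terms of all AEs, but it maps verbatim text to the dictionary and does not count events by arm.

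**2. Length of the window for completers**

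Take the stop date as the Visit 7 date, because protocol 5.1 has the last dose given in clinic at that visit. The contact falls on day 6 to day 11, nominally day 7. Days from stop + 2 to the contact are contact day - 1: 5 to 10 days, nominally 7 - 1 = 6. SAP 11.5.1.5.2 gives the same 6 days (study conclusion - end of treatment - 1).

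Share of a year: 6/365.25 = 1.6% (5/365.25 = 1.4%; 10/365.25 = 2.7%).

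**3. Expected events in the window**

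Formula: subjects x days/365.25 x 12-month incidence, at constant hazard. The incidences are those quoted in protocol 1.3.1 from two earlier FF/VI studies: pneumonia 6 to 7% with FF/VI and 3% with VI alone; fractures 2% with FF/VI and under 1% with VI. I assume that the triple arm behaves like FF/VI, that UMEC/VI behaves like VI alone, and that all 10,000 subjects complete.

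- All subjects: 10,000 x 6/365.25 = 164.3 subject-years.
- FF arms: 8,000 x 6/365.25 = 131.4 subject-years. Pneumonias: 131.4 x 0.06 = 7.9 to 131.4 x 0.07 = 9.2.
- UMEC/VI: 2,000 x 6/365.25 = 32.9 subject-years. Pneumonias: 32.9 x 0.03 = 1.0.
- Fractures: 131.4 x 0.02 = 2.6 in the FF arms, and under 32.9 x 0.01 = 0.3 in UMEC/VI, so about 3 in all.

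Over the 5 to 10 day range, pneumonias in the FF arms run from 8,000 x 5/365.25 x 0.06 = 6.6 to 8,000 x 10/365.25 x 0.07 = 15.3. In UMEC/VI they run from 0.8 to 1.6. Converting incidence to a hazard with -ln(1 - p) changes the nominal 7.9 to 9.2 only to 8.1 to 9.5.

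These counts include serious events, which are already in the SAE tables. The documents give no split by seriousness, so the number missing from every incidence table is some unknown part of them.

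**4. Does the omission distort the on-treatment rates?**

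The on-treatment numerator stops at stop + 1. So does the on-treatment at-risk period in 11.5.1.5.2, and so does censoring in 11.5.4.8. Events and person-time are cut at the same point.

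**The case against.** The strongest reply is that the protocol sentence says less than it seems to. Read literally it would also require a pre-treatment table of all AEs. Yet AEs are collected only from Visit 2, and before that only SAEs (related ones, or all in China). It may simply mean that phases are not pooled, with the detail left to the RAP. This has some force for the pre-treatment phase. For the post-treatment phase, though, AEs are collected, and leaving detail to the RAP does not cover dropping a stated summary in silence. It does stand that the protocol gives no post-treatment window for pneumonia, cardiovascular or fracture displays, so tables running to stop + 7 would be an addition and not a restored commitment.

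Three stronger readings are tempting, and the documents do not support them.

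- *A reader might infer that someone who stops the inhaler while falling ill and is diagnosed days later drops out of the pneumonia tables.* Phase follows onset date, not diagnosis date. Onset up to stop + 1 stays on-treatment however late it is reported, and under SAP 11.6.1 an event whose phase is uncertain defaults to on-treatment. Subjects are also encouraged to stay on IP until the discontinuation visit, where AEs are assessed.
- *A reader might infer that the on-treatment comparisons are biased.* Step 4 shows numerator and person-time ending together, and the documents give no figure for onset clustering just after stopping.
- *A reader might infer that the stop + 7 rule for deaths contradicts the stop + 1 rule for AEs.* SAP 11.3.2 is a separately defined phase for the mortality endpoint. A fatal event with onset on day +3 and death on day +5 is an on-treatment death there, and it still appears in Table 3.027. The labels differ; the event is not lost.

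**Conclusion.** The point holds as an unmet and undeclared reporting commitment of small expected size. The protocol states a post-treatment summary of AEs and SAEs; the SAP supplies it for serious events only. SAP 2.1 is silent. Nothing is lost from the database or the listings, and no endpoint, on-treatment rate or rate ratio is shown to be wrong.

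The nominal counts in the brief rest on a constant hazard, the earlier studies' incidences and full completion. Subjects who stop early may have a longer window, because the safety contact is timed from the discontinuation visit and 6.3.9 read literally runs to Visit 7. The documents give no basis for sizing that part.

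The conflict between protocol 6.3.9 on one side and 4.4.2 and Table 4 Note 1 on the other is real and separate. It concerns what is collected, not how it is displayed.

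**What to change.** 1. Add a post-treatment AE table by arm covering all AEs, with the pneumonia, cardiovascular and fracture special-interest groups shown. Use the post-treatment at-risk period in SAP 11.5.1.5.2 for rates. If the sponsor prefers not to, declare and justify the omission in SAP 2.1.
2. Optionally, add supplementary incidence tables for pneumonia, cardiovascular events and fractures with onset through stop + 7. Leave the on-treatment analyses as they are.
3. Reconcile protocol 6.3.9 with 4.4.2 and Table 4 Note 1, in one sentence, so that all sites collect the same events after early discontinuation of IP.

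The cost is a few tables on data already collected up to the 7-day contact, plus the clarifying sentence. The downside is slightly higher reported event counts.
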